9.3.1.1. Duration of Mysimba/Contrave Use

Duration of Mysimba/Contrave use will be determined based on prescription or dispensing data (depending on availability in the data source). The days' supply for each prescription will be used to determine the days of medication covered by that prescription. If days' supply is unavailable for a prescription or dispensing, it will be imputed as the mode for the most granular medication variable level available (e.g., by National Drug Code [NDC] in U.S. data, ATC in Nordic data) for the database. The count of duration (days) will include all days during which medication was available without accounting for overlap (i.e., no stockpiling will be included in the duration), a gap of up to half of the days' supply of the immediately preceding prescription, and a wash-out after the end of the last prescription days' supply (Figure 2). After the initial episode of Mysimba/Contrave duration, the duration of any subsequent episodes will also be captured.

[figure not shown]
Duration will be assessed in two ways:

- 1. Continuous treatment in the initial Contrave duration: the number of days duration in the initial Contrave episode (two continuous treatment episodes are in Figure 2; the first is 106 days and the second is 45 days [225-180 days])
- 2. Total duration of Mysimba/Contrave: the number of days duration in the 548 days (18 months) after the index Mysimba/Contrave prescription (the total duration of Mysimba/Contrave use in Figure 2 is 106+45 =151 days)

For Mysimba, similar calculations will be done, except that the day's supply will be 28-days after titration.

[figure not shown]
Figure 2. Duration of Mysimba/Contrave Use Episodes

U.S. Contrave

accounted for in the analysis

Nordic Countries

initial prescription or dispensing is 38 ½ day supply which includes 28 days for titration. Each dispensing is 112 pill count. Stockpiling will not be accounted for in the analysis

In addition, the number of prescriptions, number and duration of treatment episodes and duration between treatment episodes will be described.

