All citizens of these countries are represented in these national registries until death or emigration, providing virtually complete long-term follow-up. Identification of individuals by their unique personal identifier permits linkage to other national health databases (Laugersen et al., 2021). Thus, a large amount of specialized information from specific registries, such as hospitalization, prescription, heart disease, and death registries, can be linked for research (Schmidt 2015; Laugersen et al., 2021). The registries are highly complete and accurate due to the automation of their processes, as well as laws and other incentives motivating healthcare providers to collect and send the data electronically to their national databases (Gribsholt et al., 2019). The data from each country are expected to contain sufficient information to elucidate occurrence and determine levels of all variables, with the following exceptions which may be prone to misclassification due to limited coding in administrative and clinical data: obese or overweight with at least one comorbidity, neuropsychiatric conditions, history or current substance use or dependence, breastfeeding status, initial titration scheme and dose adjustments (expected to be unavailable since only one dose/pack type is available in the Nordic countries and no measure of titration scheme or adherence is included within the data), and reason(s) for medication discontinuation. Any country database with at least 750 patients with at least 365

days of data before the index Mysimba use and at least 548 days of availability in the data after the index date of Mysimba will be evaluated for whether there is sufficient required patient data to conduct this study. If there is sufficient data and uptake indicating that the database will reach more than 3,000 patients within the timespan of this drug utilisation and safety study, then it will be added to the data sources for evaluation. It should be noted that reimbursement varies in Scandinavia, with no reimbursement for Mysimba in Sweden and Denmark, and reimbursement in Norway and Finland restricted to morbidly obese patients who are at higher risk of cardiovascular and other events.

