The proportion of users non-adherent to each component of the indication/contraindications will also be determined. Small numbers will be presented as "<x" where "x" represents the defined threshold for the smallest number of patients that is allowed to be presented from the data source. Since information on the titration scheme is expected to be sparse (and, not present in the Nordic data), a sensitivity analysis will also be conducted where the first dispensing (112 tablets) is allowed to cover the full time of titration (i.e., 7 tablets in first week (n=7 days), 14 tablets in second week, 21 tablets in third week, and the remaining 70 tablets over 17.5 days (4 tablets per day) for a total of 38.5 days). The possible gap will be 19 days (half of the days' supply) before the second dispensing. Duration of Mysimba/Contrave use and adherence will be recalculated based on this adjustment. Adherence to the titration scheme will be confirmed for a patient if the second dispensing occurs within 40 days +/- 7 days from the first dispensing. Additionally, another sensitivity analysis will be implemented in which patients with evidence of renal or liver impairment are allowed up to 56 days for consumption of *each* dispensing to account for

continued use and adherence within these patients who are unlikely to reach the full recommended dosage due to renal or hepatic dosage adjustments.

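### A second dispensing on days 33 to 47 cannot confirm titration: 10 of the 15 qualifying days also fit full-dose use from day 1, and some titrators fail the rule

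*Protocol*

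**What the plan says.** Section 9.7.2 introduces a sensitivity analysis because titration information is expected to be sparse, and absent from the Nordic data. It lets the first 112-tablet dispensing cover the titration period: "7 tablets in first week (n=7 days), 14 tablets in second week, 21 tablets in third week", then "the remaining 70 tablets over 17.5 days (4 tablets per day) for a total of 38.5 days". It adds: "The possible gap will be 19 days (half of the days' supply) before the second dispensing". It then fixes the classification rule: "Adherence to the titration scheme will be confirmed for a patient if the second dispensing occurs within 40 days +/- 7 days", counted from the first dispensing.

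Section 9.4.1 says of the Nordic registries that "no measure of titration scheme or adherence is included within the data". Appendix 3 shows no Nordic entry for initial titration scheme or dosing during titration, and only a possible entry for the US.

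For continuous use, Section 9.3.1.1 allows "a gap of up to half of the days' supply of the immediately preceding prescription". For Nordic packs it states "Each dispensing is 112 pill count", with 28 days' supply after titration. Section 9.3.1.2 assumes 4 tablets a day in the primary analyses when dose is not recorded.

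Section 8 makes the initial titration scheme, and the proportion aligned with the SmPC, a secondary objective to the extent the data allow. Section 9.7.4 calculates that proportion among patients with available information.

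**The concern.** The rule turns one observation, the interval between the first two dispensings, into a statement about how the tablets were taken in between. The same interval can arise from titration with a punctual refill, from full-dose use with a late refill, or from a constant lower dose. The protocol does not say how these are told apart.

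If the rule is followed as written, some patients who never titrated will be reported as confirmed adherent, and some who titrated exactly as scheduled will be reported as not adherent. For the Nordic sources no other titration measure exists. Any Nordic titration figure would therefore rest on this rule alone, and a reader could take it as the SmPC-alignment result named in the secondary objective.

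**Working it through.** **Inputs, all from the protocol.** Pack of 112 tablets (9.3.1.1, 9.7.2); titration use of 7, 14 and 21 tablets in weeks 1 to 3, then 4 a day (9.7.2); full-dose use of 4 a day (9.3.1.2); gap of half the preceding supply (9.3.1.1); 19-day gap after a titrated first pack (9.7.2); window of 40 ± 7 days (9.7.2).

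**1. The protocol's own figure.** Titrated first pack: 7 + 7 + 7 + (112 − 42)/4 = 21 + 17.5 = 38.5 days. Half of that is 19.25, stated as 19. Both figures reproduce.

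**2. The window.** 40 − 7 = 33 and 40 + 7 = 47, which is 15 whole days.

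**3. A patient who never titrates.** Supply 112/4 = 28 days; gap 28/2 = 14 days; latest refill without a break 28 + 14 = day 42. Days 33 to 42 lie in both ranges: 10 of 15 days. Days 43 to 47 lie beyond this patient's gap limit.

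**4. Other departures from the schedule, refilled exactly when the pack is empty.**

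| Pattern | Pack empty | In window? |
|---|---|---|
| Constant 3 a day | 112/3 = day 37.3 | Yes |
| 1 a day in week 1, then 4 a day | 7 + 105/4 = day 33.25 | Yes |
| Weeks 1 and 2 as scheduled, then 4 a day | 14 + 91/4 = day 36.75 | Yes |
| Weeks 1 and 2 as scheduled, then 3 a day | 14 + 91/3 = day 44.3 | Yes |

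These need no assumption about refill delay.

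**5. A patient who titrates as scheduled.** Latest refill without a break: 38.5 + 19 = 57.5, so whole day 57. Refills on days 48 to 57 are continuous use but fail the titration rule. So do refills before day 33.

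**6. Illustration of size.** The documents give no refill-delay distribution, so both models below are assumptions.

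*Normal refill time, SD 7 days, mean 38.5 + d (titrators) or 28 + d (non-titrators), whole-day limits 32.5 to 47.5.* At d = 0, titrators: Φ(9/7) − Φ(−6/7) = 0.71; non-titrators: Φ(19.5/7) − Φ(4.5/7) = 0.26.

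| Mean delay d (days) | Titrators classed as adherent | Non-titrators classed as adherent |
|---|---|---|
| 0 | 71% | 26% |
| 3 | 71% | 41% |
| 5 | 66% | 51% |
| 7 | 58% | 60% |

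*Exponential delay with mean m after the pack is empty, limits 33 and 47.* Titrators: 1 − exp(−8.5/m). Non-titrators: exp(−5/m) − exp(−19/m).

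| Mean delay m (days) | Titrators | Non-titrators |
|---|---|---|
| 3 | 94% | 19% |
| 7 | 70% | 42% |
| 14 | 46% | 44% |

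Separation is good when delays are short and vanishes when they are long.

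**The case against.** The protocol is open about the limitation. Section 9.7.2 repeats what Section 9.4.1 says and offers the refill rule as a proxy inside a sensitivity analysis. Section 8 qualifies the titration objective by data availability, and Section 9.7.4 restricts the proportion to patients with information. Titration is not among the non-compliance categories listed in Section 9.7.2, and AESI person-time in Section 9.7.3 does not use the rule. The gap rule defines continuous treatment, not titration, and a count of overlapping days is not a count of misclassified patients.

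All of this stands, and it limits the point. A reader might infer that the whole 33 to 47 day window is open to non-titrators; with a 28-day supply the limit is day 42. A reader might also infer that the resulting proportion is uninterpretable, or that the rule never discriminates; that holds only under long assumed delays, and a punctual full-dose refill near day 28 fails the rule as it should. Nor does any section say that the refill rule supplies the Section 9.7.4 proportion for Nordic patients; the text merely leaves that open.

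What the objection does not answer is the classification itself. The proxy is worded as confirmation, and the protocol's own supply figures show that it cannot confirm.

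**Conclusion.** The point holds in a limited form. By arithmetic from the protocol alone, 10 of the 15 qualifying days are compatible with never having titrated, and several partly titrated or constant-dose patterns land in the window with no delay at all. In the other direction, days 48 to 57 and any day before 33 exclude patients who may have titrated as scheduled.

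The share of patients misclassified cannot be derived from the documents, because it depends on refill delay and on how many patients do not titrate; the percentages above illustrate the dependence and are not estimates. The consequence is confined to what may be concluded about titration, chiefly in the Nordic sources.

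A related inconsistency bears on the calculation. Section 9.3.1.1 describes the Nordic initial dispensing as a 38½-day supply, whereas Section 9.7.2 uses 38.5 days only in a sensitivity analysis. If 38.5 days were credited to every Nordic patient, the continuous-use limit would be day 57 for all, and the whole window would lie inside it.

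**What to change.** In Section 9.7.2:

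- Replace the statement that adherence will be confirmed with one that refill timing will be classed as compatible with titration.
- Report the distribution of days from first to second dispensing, with 28 and 38.5 days marked.
- Report patients with no second dispensing as not assessable.
- State that misclassification runs in both directions: late refills after full-dose or constant lower-dose use pass, while titrators refilling before day 33 or on days 48 to 57 fail.
- State that this proxy does not supply the SmPC-alignment proportion of Sections 8 and 9.7.4, which stays limited to sources with recorded titration.

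Reconcile Sections 9.3.1.1 and 9.7.2 on whether the 38.5-day first supply belongs to the main Nordic analysis or only to the sensitivity analysis.

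The cost is a change of wording and one descriptive display from data already extracted. The downside is that no Nordic titration-adherence percentage can be claimed.

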9.7.3. Incidence Rate of AESIs

The incidence rate of AESIs per person-years of exposure after initiation of Mysimba/Contrave will be assessed. Person-time of exposure will be calculated as the duration from the index date through the date of last Mysimba/Contrave prescription or dispensation (i.e., total treatment duration of Mysimba/Contrave), as applicable, plus 4 weeks. The number of cycles of Mysimba/Contrave during the exposure period will be summarized comparing all users, irrespective of their treatment duration status.

For each type of AESI, the crude incidence of new AESIs will be reported and the incidence proportion and 95% CI of will be estimated as the number of patients experiencing each type of event during Mysimba/Contrave exposure divided by the number of patients initiating treatment with Mysimba/Contrave. The proportion will be reported per 1,000 persons. The incidence density rate and 95% CI of AESI will be reported per 1,000 per person-years, using the sum of the person-years of the at-risk population as the denominator.

Further, clinical events of interest that might be associated with the occurrence of a potential AESI (e.g., newly initiating anti-epileptic/seizure medication, newly initiating medications indicated for mania or depression) will also be tabulated. For hepatotoxicity, liver function tests can be used (when available) in addition to diagnostic codes.

For reason(s) patients who discontinue treatment (i.e., do not refill their prescription), clinical events and health status occurring within the 90-day window prior to discontinuation will be summarized.

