9.7.3.1. Incidence Rates of AESIs in Subgroups of Patients

If data are available and appropriate predictors are available in the respective database, sensitivity analyses around the definition of each type of AESI will be performed. Incidence proportion and density of each type of AESI will also be calculated for the subgroup of patients compliant or non-compliant with the EU SmPC (as listed in section 9.7.1, the criteria will be adapted for the relevant country of the data source stems if the SmPC differ across such countries, i.e., for U.S.), including relevant comorbidities, concomitant medications, and pregnancy. Adaptations will be made if BMI is not available; these will be described in the SAP. The incidence rate (and 95% CI) of new onset comorbidities and concomitant medication after initiation of Mysimba/Contrave will be assessed. Incidence rates will be determined both for the person-years of time exposed to Mysimba/Contrave (i.e., while patient taking medication) after the index date as well as for all person time through 548 days after the index Mysimba/Contrave prescription.

The incidence rate (and 95% CI) of pregnancy and breastfeeding after the Mysimba/Contrave index date will be assessed among females initiating Mysimba/Contrave. These analyses will be conducted in data sources where the necessary variables are present.

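### AESI exposure in section 9.7.3 is one unbroken span that takes in treatment gaps, but section 9.3.1.1 defines the quantity it is equated with as a sum of episodes

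*Protocol*

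**What the plan says.** Section 9.7.3 sets the exposure time for AESI rates: "Person-time of exposure will be calculated as the duration from the index date through the date of last Mysimba/Contrave prescription or dispensation". It continues: "i.e., total treatment duration of Mysimba/Contrave), as applicable, plus 4 weeks". Events are counted during that exposure, and the incidence density is formed "using the sum of the person-years of the at-risk population as the denominator".

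Section 9.3.1.1 defines total duration differently. Days of supply are joined into episodes. A gap is bridged only up to half of the preceding supply, a wash-out is added after the last supply, and the episodes are then summed. Its worked example has two episodes: "the first is 106 days and the second is 45 days [225-180 days". The result is: "the total duration of Mysimba/Contrave use in Figure 2 is 106+45 =151 days". Days 106 to 180 are not counted.

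Section 9.7.3.1 and the synopsis use a third wording, "the person-years of time exposed to Mysimba/Contrave (i.e., while patient taking medication", in a sentence that follows the one on new comorbidities and concomitant medication.

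On the first Nordic fill, the text beside Figure 2 says: "initial prescription or dispensing is 38 ½ day supply which includes 28 days for titration". Section 9.7.2 presents the same 38.5 days as a departure from the main analysis: "a sensitivity analysis will also be conducted where the first dispensing (112 tablets) is allowed to cover the full time of titration". Section 9.3.1.2 assumes 4 pills a day in primary analyses when no dose is recorded.

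**The concern.** The protocol gives one name to two different quantities, and the AESI rates use the one that counts untreated time. Gaps are expected: section 9.3.2 chooses the 548-day window so that multiple cycles can be seen, and section 9.7.3 itself counts cycles.

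The 9.7.3 span also depends on the future. If a patient stops, exposure ends 28 days after the last fill. If the same patient refills months later, the whole interval becomes exposed in retrospect. The patient must be alive to refill, so for completed suicide and cardiovascular death, both named AESI components, the gap can add person-time but never an event. For non-fatal AESIs, an event in a gap counts if the patient later restarts and does not count if treatment never resumes.

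These rates serve the secondary objective that compares AESIs between users compliant and non-compliant with the SmPC. If interruption patterns differ between those groups, the misclassification enters the comparison. Reported treatment duration (objective 5 in the synopsis) and AESI exposure would also fail to reconcile within one report.

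**Working it through.** **1. Reproduce the protocol's figure (9.3.1.1).** Second episode: 225 − 180 = 45 days. Total: 106 + 45 = 151 days. This agrees with the text.

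**2. Apply the 9.7.3 rule to the same patient.** Exposure = day of last fill + 28. Figure 2 is not shown, so the last fill day is an assumption. Day 180 fits a 30-day supply plus a 15-day wash-out, which gives the stated 45 days. Day 197 is the fill day at which the rule ends with the episode, since 197 + 28 = 225.

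| Last fill | 9.7.3 days | Ratio to 151 | 151 / 9.7.3 days |
|---|---|---|---|
| Day 180 | 208 | 1.38 | 0.73 |
| Day 197 | 225 | 1.49 | 0.67 |

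The gap is 180 − 106 = 74 days, or 74/208 = 36% of the span in the first row. In that row the rule also drops days 208 to 225 (17 days), which 9.3.1.1 counts as exposed. The last column is the ratio of the two rates only if the number of counted events is the same under both rules.

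**3. Effect on a non-fatal AESI rate in this patient.** With the last fill on day 180, the 208 days are 106 + 28 = 134 days inside episodes and 74 in the gap. Gap events are counted, because the patient refills. If the hazard on drug is h times the hazard off drug, the 9.7.3 rate divided by the on-drug rate is (134h + 74) / (208h).

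- h = 1: 208/208 = 1.00
- h = 2: 342/416 = 0.82
- h = 3: 476/624 = 0.76

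With the last fill on day 197 and h = 2, it is (302 + 74)/450 = 0.84.

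**4. Dependence on the gap.** Take two 28-day fills. The text does not give the wash-out length, so assume 14 days per episode. Once the second fill falls after day 42, 9.3.1.1 gives 2 × (28 + 14) = 84 days whatever the gap. The 9.7.3 rule gives 84 days if the second fill is on day 56, 112 on day 84, 208 on day 180 and 393 on day 365.

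**5. Users without gaps.** Under the same assumptions the sign reverses.

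- One fill: 28 days under 9.7.3 against 28 + 14 = 42 under 9.3.1.1 (ratio 0.67).
- Six consecutive fills: 5 × 28 + 28 = 168 against 6 × 28 + 14 = 182 (ratio 0.92).

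In an illustrative mix of single-fill patients (share p) and Figure 2 patients, total person-time is equal when 14p = 57(1 − p), so p = 57/71 = 0.80. The document gives no such mix.

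**6. First-fill supply.** Section 9.7.2 uses 7 + 14 + 21 = 42 tablets in 21 days, then (112 − 42)/4 = 17.5 days, for a total of 38.5 days. At 4 pills a day throughout, 112/4 = 28 days. With half-supply bridging, the window to the second fill is 28 + 14 = 42 days or 38.5 + 19 = 57.5 days. If 38.5 days applies, a one-fill patient leaves 9.7.3 exposure with 38.5 − 28 = 10.5 days of supply left. If 28 days applies, the tail equals the supply.

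**The case against.** The best defence is that a single span to the last fill plus a short tail is a simple and common exposure window, and that what is at issue is mainly a label. Several parts of this defence stand.

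- A reader might infer that the added gap time is free of events. It is not: section 9.7.3 counts events during its exposure span, and a non-fatal event in a gap followed by a refill is included. A refill guarantees only survival.
- A reader might infer that AESI rates are understated overall, by 27% (1 − 151/208). The document does not support this. The figure belongs to one illustrative patient, rests on an assumed fill date, holds the event count fixed, and becomes zero when hazards are equal. For single-fill and uninterrupted users the 9.7.3 rule can shorten the denominator.
- The 151 days are not pure drug-taking time, because 9.3.1.1 includes bridged gaps and a wash-out.
- The wording in section 9.7.3.1 may apply only to comorbidities and concomitant medication, so it is weak evidence of a third AESI definition.
- The 38.5-day text is a fragment beside a missing figure, and AESI incidence is a secondary objective in a study without prior hypotheses.
- An episode-based rule would also leave an event in a permanent gap out of the on-treatment rate.

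The conflict survives all of this. Section 9.7.3 does not merely choose a window; it equates the window with a quantity defined otherwise in 9.3.1.1, and nothing reconciles them. The limitation in section 9.9.1 concerns the 548-day window, not gaps inside the span called exposed. Equal total person-time would not help either, since untreated days would stand in for treated ones. An episode-based rule treats a gap event alike whether or not the patient restarts.

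**Conclusion.** The point holds as a conflict of definitions with a real consequence for AESI rates. In the protocol's own example, exposure is 151 days under 9.3.1.1 and 208 under 9.7.3 (225 if the last fill is on day 197), and 74 of those days are untreated. In such patients the gap is immortal time for fatal AESIs. For non-fatal AESIs the rate moves towards the off-drug rate, by an amount set by the hazard ratio. The hazards in that calculation are assumptions and are constant within on-drug and off-drug time.

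The direction and size for the whole cohort cannot be derived, because they depend on the mix of interrupted, uninterrupted and single-fill users and on the wash-out length. What is certain is that exposed time is misclassified under the stated rule and that AESI exposure will not agree with reported treatment duration. The first-fill supply is a secondary point: sections 9.3.1.1, 9.3.1.2 and 9.7.2 must be reconciled on it.

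**What to change.** - In section 9.7.3, use the episode-based exposed time of 9.3.1.1, with one stated risk tail after each episode, for both events and person-time in the on-treatment AESI rates. Use the same definition in section 9.7.3.1 and the synopsis.
- Report person-time and events between episodes, and after the last one, as a separate unexposed category, so that nothing is lost and restarting does not decide how a gap is classified.
- Keep the span from index to last fill plus 4 weeks, if wanted, as a sensitivity analysis under its own name, not as total treatment duration.
- State once whether the 28-day or the 38.5-day first-fill supply is the primary exposure assumption, and make the other the sensitivity analysis.

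The cost is wording and a small amount of programming. On-treatment person-years and confidence intervals may move in either direction, depending on the mix of users.
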